1 PROTOCOL SUMMARY

1.1 SYNOPSIS

Title: PAZAZ: Personalized azithromycin/metronidazole, in combination with standard induction therapy, to achieve a fecal microbiome community structure and metagenome changes associated with sustained remission in pediatric Crohn's Disease (CD)-- a pilot study

Study Description: This is a multi-center, randomized, controlled open-label add-on design trial pilot study to evaluate the efficacy of personalized adjunctive antibiotic (azithromycin + metronidazole) therapy in pediatric subjects with mild to moderate Crohn's disease (CD) who have a relapse-associated microbiome profile. The study hypothesis is that adjunctive antibiotic therapy will improve clinical response to standard of care (SOC) induction therapy in a subgroup of CD patients with a relapse-associated microbiome profile. This is an add-on design trial for subjects already receiving SOC induction therapy; there will be no placebos.

Prior to starting SOC induction therapy at week 0, subjects will provide a baseline stool sample that will be screened for microbiome profiles associated with risk of relapse according to an established statistical model.

At week 4, subjects with a relapse-associated microbiome will be randomized into either a control arm that will continue to receive SOC induction therapy for an additional 8 weeks, or a treatment arm that will receive adjunctive antibiotic therapy in addition to continuing to receive SOC induction therapy for an additional 8 weeks. Subjects who do not have a relapse-associated microbiome will enter a separate control arm that will continue to receive SOC induction therapy and will have data collected for exploratory objectives. Subjects who are not in clinical

remission by week 4 will receive antibiotic therapy regardless of microbiome signature at baseline. Subjects will be monitored for an additional 40 weeks after the treatment period (52 weeks total).

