2.3.3 ASSESSMENT OF POTENTIAL RISKS AND BENEFITS

The available information suggests that the present clinical study has an acceptable risk-benefit ratio.

Approximately 50% of pediatric patients with CD will relapse within a year of starting induction therapy and require repeated courses of induction therapy and/or treatment escalation.^{41,42} Subjects in the antibiotic treatment arm of this trial will continue to receive standard therapy and are at comparable risk of relapse as subjects in the control arms. In group C of subjects not achieving remission with nutritional induction therapy alone, there will be no randomization and antibiotics will be given as additional induction treatment. The patient, parents and treating physician are free at all times to choose any treatment outside of the study.

The risk of rare, but serious, heart-related side effects from the antibiotic drug azithromycin are minimized by screening patients for heart rhythm irregularities prior to administering antibiotics. Metronidazole presents minimal risk to the subjects and is routinely used in this pediatric population. The safety monitoring practices employed by this protocol are adequate to protect the subjects' safety and detect all anticipated adverse events.

Subjects in the antibiotic intervention arm may experience direct health benefit through the study treatment by reducing their risk of disease flare thus avoiding additional intestinal damage as well as additional immune suppression or surgery. There will be no additional direct benefit for subjects in the reference arms because they will be receiving standard care. The knowledge gained from this trial could lead to improved treatment approaches for a subgroup of patients who have a relapse-associated microbiome profile.

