3 OBJECTIVES AND OUTCOME VARIABLES

OBJECTIVES	OUTCOME VARIABLES	JUSTIFICATION FOR OUTCOME VARIABLES
Primary		
To evaluate the potential efficacy of personalized adjunctive antibiotic therapy in maintaining clinical remission in pediatric subjects undergoing SOC induction therapy for mild to moderate Crohn's disease who have a relapse-associated microbiome profile	Proportion of subjects in sustained remission at 52 weeks after starting standard of care induction therapy Sustained remission is defined PCDAI less than or equal to 10 AND no need of re-induction for clinical flare (new course of EEN, need to restart steroids), no steroid dependence, no biologic (anti-TNF) use, and no intestinal surgery by 12 months.	We will aim to demonstrate superiority of adjunctive antibiotic therapy + SOC over SOC alone in patients with a relapse-associated microbiome. Group A1 and A2 will be compared and sustained remission is the principal analysis variable.
Secondary		

OBJECTIVES	OUTCOME VARIABLES	JUSTIFICATION FOR OUTCOME VARIABLES
To evaluate the potential efficacy of personalized adjunctive antibiotic therapy in improving PRO, components of established disease activity measures in remission, as well as 'biochemical' remission in pediatric subjects undergoing SOC induction therapy for mild to moderate Crohn's disease who have a relapse-associated microbiome profile	
Longitudinal (clustered and with respect to baseline) changes in disease activity indices (PCDAI) components, and inflammatory markers in blood and stool:
 
 • PCDAI score (0-100) • Normalization of CRP (mg/dL) • Fecal calprotectin (FCP) (microgram/g) 
Longitudinal (clustered and with respect to baseline) changes PRO:
 
 • IMPACT (self-report, ages 9-17 years) 	Multiple secondary variables are needed to describe clinically relevant treatment benefits. Depending on the results of the microbiome analysis, either groups A2 and B will be pooled and compared with group A1 or groups A1 and B will be pooled and compared with group A2 (section 9.4.3).
Tertiary/Exploratory		

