4 STUDY DESIGN

4.1 OVERALL DESIGN

The primary hypothesis tested is that administering adjunctive antibiotic therapy to patients with a relapse-associated gut microbiome profile will help to sustain clinical response to standard induction therapy for mild to moderately active Crohn's disease.

To test this hypothesis, patients with a relapse-associated microbiome profile will be identified via baseline stool sample analysis and will be randomly allocated to the treatment arm that will receive antibiotics (azithromycin + metronidazole) on top of SOC induction therapy, or a control arm that will receive SOC induction therapy alone. Patients not achieving clinical remission (PCDAI greater than 10 at week 4), can receive antibiotics (azithromycin/metronidazole), will not be randomized, and will continue to be followed until 52 weeks. This pilot trial is intended to be a smaller version of a larger trial, and will be used to evaluate feasibility including standard deviation of the outcome measures, adherence, and baseline microbiome profiling.

Standard of care (SOC) induction therapy, as started by the responsible physician, for this study will be defined as Crohn's Disease Exclusion diet nutritional therapy (CDED Phase 1 from 0-6 weeks and Phase 2 from 6-12 weeks), in accordance with the recently published RCT for the CDED.²⁴

This is a 52-week, multicenter, randomized, controlled, open-label add-on design clinical trial pilot trial to test the feasibility of a larger trial evaluating the efficacy of adjuvant antibiotic therapy in pediatric patients with mild to moderate CD. This study will not be blinded.

A total of 20 subjects between the ages of 3 and 17 years inclusive will be enrolled in eight investigational sites located in Canada, the United States, the Netherlands and Israel.

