9 STATISTICAL CONSIDERATIONS

9.1 STUDY OUTCOME VARIABLES

The primary outcome evaluation:

The primary efficacy outcome variable is being in sustained remission defined as PCDAI ≤ 10 at 52 weeks from start of therapy AND without steroid dependence and without the need for repeat induction therapy, anti-TNF α , or surgery by 52 weeks from start of therapy.

The secondary outcome evaluations at each study visit include:

- Mean change in PCDAI score from baseline to weeks 4, 12, 24, 36, and 52.
- Mean change in Inflammatory markers: CRP and fecal calprotectin from baseline to weeks 4, 12, 24, 36, and 52.
- Mean change in PRO score (IMPACT questionnaire) from baseline to weeks 4, 12, 24, 36, and 52.
- Improvement (yes vs no) of disease activity (change in PCDAI < 0) rate at weeks 4, 12, 24, 36, and 52.
- Improvement (yes vs no) of C-Reactive Protein (change in CRP < 0 mg/dL) and fecal calprotectin (change in FCP < 0 µg/g) rate at weeks 4, 12, 24, 36, and 52.
- Normalization (yes vs no) of disease activity (PCDAI < 10) rate at weeks 4, 12, 24, 36, and 52.
- Normalization (yes vs no) of C-Reactive Protein (CRP; < 0.5 mg/dL) and fecal calprotectin (FCP; < 250 µg/g) rate at weeks 4, 12, 24, 36, and 52.

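### Primary failure events are timed from week 0 although randomisation is at week 4, and no rule covers an event in between

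*Combined protocol and SAP*

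**What the plan says.** **Outcome clock.** Section 9.1 asks for a PCDAI of 10 or less at week 52, without steroid dependence and without repeat induction, anti-TNF "or surgery by 52 weeks from start of therapy". Section 3 ties the endpoint to the same origin: "Proportion of subjects in sustained remission at 52 weeks after starting standard of care induction therapy". For the failure events, sections 3, 8.1 and 9.4.2 and the addendum's objectives table give an end date of 12 months and no start date.

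**Start of therapy and allocation.** The synopsis puts the start at week 0 ("Prior to starting SOC induction therapy at week 0, subjects will provide a baseline stool sample") and allocation four weeks later ("At week 4, subjects with a relapse-associated microbiome will be randomized into either a control arm").

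**Gate at week 4.** Section 4.1 says "Patients not achieving clinical remission (PCDAI greater than 10 at week 4), can receive antibiotics" and are not randomised. Section 9.2 uses the same cut-off. Neither asks how remission was reached. Sections 2.3.3 and 4.2 instead describe the non-randomised Group C as children who did not remit on nutritional therapy alone. The other condition for Group A is the baseline microbiome signature (4.1).

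**Other treatment before week 4.** Section 2.3.3 states: "The patient, parents and treating physician are free at all times to choose any treatment outside of the study". Steroid use and EEN are not exclusion criteria in 5.2. Biologic use and intestinal resection are, and 7.2 allows an investigator to withdraw a child who newly meets an exclusion criterion. The schedule in 1.3 reviews eligibility at screening and week 0 only, but concomitant medication at every visit.

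**Analysis.** The primary comparison is A1 against A2 in all randomised children (9.3), by Fisher's exact test (9.4.2).

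**The concern.** An event that precedes allocation cannot be prevented by the allocated treatment. Take a child with the relapse-associated signature who starts steroids or a new EEN course in week 2 and has a PCDAI of 10 or less at week 4. That child passes the gate as worded in 4.1 and 9.2, is randomised, stays in the ITT set, and on the plain reading of 9.1 has already failed.

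Each such child is a non-responder in whichever arm is drawn, so the contrast shrinks. In the pilot, 20 children are shared among Groups A, B and C, so an arm can hold 10 at most, and one such child moves that arm's remission rate by at least 10 points (1/10).

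The definition also outlives the pilot. The addendum keeps sustained remission as a primary outcome beside feasibility, and allows pilot data to be included in the full-scale trial if the protocol is not substantially changed.

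**Working it through.** **1. Reproduce the planned size.** Inputs from 9.2: flare risk 80% against 40%, 80% power, 10% dropout. From 9.4.1: two-sided 0.05. From 6.3: 1:1 allocation.

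Pooled formula: n = [1.96·√(2·0.6·0.4) + 0.8416·√(0.8·0.2 + 0.4·0.6)]² / 0.4² = (1.358 + 0.532)² / 0.16 = 22.3, so 23 per arm. Dividing by 0.9 gives 26. The arcsine formula gives 22, and 22/0.9 = 24.4, so 25. The stated 25 per arm is therefore reproduced, and it leaves 25 × 0.9 = 22.5, about 23 evaluable per arm.

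**2. Insert pre-randomisation failures.** Let f be the share of randomised children who already had a listed event. The documents give no value, so f is an assumption. If 80% and 40% apply to the remaining children:

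- failure in A1 = f + (1 − f)·0.8
- failure in A2 = f + (1 − f)·0.4
- difference = 0.4·(1 − f)

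| f (assumed) | A1 failure | A2 failure | Difference | Exact Fisher power, 23 per arm | Exact Fisher power, 25 per arm | Randomised per arm for 80% power (pooled formula, 10% dropout) |
|---|---|---|---|---|---|---|
| 0 | 80% | 40% | 40 points | 72.7% | 78.8% | 26 |
| 5% | 81% | 43% | 38 points | 68.2% | 74.2% | 28 |
| 10% | 82% | 46% | 36 points | 63.7% | 69.1% | 30 |
| 20% | 84% | 52% | 32 points | 54.9% | 58.4% | 37 |

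The 23-per-arm column is the relevant one, because 25 already includes dropout. Its starting value is below 80% because the stated size matches formulas other than Fisher's test. The loss should be read against 73%. The 20% row only shows the shape of the effect.

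**3. Pilot.** In the best case of 10 against 10, Fisher power is 25% at f = 0, 23% at f = 5% and 20% at f = 10%. The pilot cannot test efficacy in any case. What matters there is the movement from a single child.

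**4. Side-by-side reading of the text.**

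- The end of the event window is fixed at 52 weeks from the start of therapy. Its start is not written.
- The steroid component varies: the synopsis and 8.1 refer to starting steroids; section 3, 9.4.2 and the addendum refer to restarting them.
- Under the 4.1/9.2 gate, a child in remission after steroids or EEN is randomised. Under the 2.3.3/4.2 description, that child has not met the stated basis for randomisation.
- Withdrawal under 7.2 can reach new biologic use and resection, but it is discretionary. It does not reach steroids or EEN.

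**The case against.** The strongest reply is that the plan already keeps such children out. Sections 2.3.3 and 4.2 frame week-4 remission as remission on nutritional therapy alone, and a child rescued with steroids has not achieved that. A reader might infer from 4.1 that no safeguard exists at all; 2.3.3 and 4.2 do not support that. What remains is that the passages giving the operative cut-off, 4.1 and 9.2, lack the condition, so sites could apply either version.

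Second, re-induction, repeat induction and restarting steroids all suggest a flare after a first induction. On that reading, treatment added during the first four weeks is not an event. This stands as an uncertainty: the text does not establish that such a child has definitely failed. But if this reading is intended, the early event is simply unclassified, and in an unblinded trial (6.3) it would be classified with the arm known.

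Third, the sentence in 2.3.3 on free choice of treatment sits in a risk-benefit discussion and does not say that a rescued child goes on to randomisation. That is fair: it leaves the route open without describing it.

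Fourth, f may be small. The child must be rescued, reach a PCDAI of 10 or less within four weeks of a mild-to-moderate start, and carry the signature. Section 9.2 also quotes background risk over the first year after diagnosis; if the 80% and 40% already include early events, applying (1 − f) counts them twice. Both points stand as limits on the size.

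Finally, the addendum says the pilot is too small for efficacy conclusions, and a one-year outcome from the start of induction is a recognisable clinical measure. Neither point supplies the missing rule.

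**Conclusion.** The concern holds as a gap in the endpoint definition combined with an inconsistent gate. The failure window is tied to the start of therapy, allocation comes four weeks later, and no text classifies an event in between. Under the plain reading of 9.1 and the PCDAI-only gate, steroid or EEN use in weeks 0–4 can enter the primary analysis as a failure unrelated to allocation. Biologic use and resection are only partly covered.

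A reader might infer a biased comparison or an inflated type I error. Neither follows: these events precede randomisation, so they are balanced between arms in expectation. The harm is dilution and, in very small arms, chance imbalance.

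The size is unknown. With f assumed at 5–10%, and 80% against 40% holding for the unaffected children, the difference falls from 40 to 38–36 points, and Fisher power at 23 evaluable per arm falls from 73% to 68–64%. Those powers belong to the later trial. The change is worth making because it is nearly free and the definition may be carried forward.

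**What to change.** In sections 3, 8.1, 9.1 and 9.4.2 and in the addendum's objectives table, count the listed failure events from the date of randomisation (week 4) to week 52. Keep the requirement of a PCDAI of 10 or less at week 52. Use one wording for the steroid component, and say how a treatment begun before randomisation and still running is classified. Report week 0–4 events descriptively by arm; the week-4 concomitant medication review already collects the treatment information.

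Separately, reconcile 4.1 and 9.2 with 2.3.3 and 4.2 on whether week-4 remission must be on nutritional therapy alone. The sponsor decides which applies; this review proposes no gate.

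The cost is a few sentences of wording. The event window becomes 52 − 4 = 48 weeks after randomisation instead of 52 weeks from the start of induction, which makes the result slightly less comparable with one-year figures counted from the start of therapy. The planned contrast and the 25 per arm in 9.2 need no change on this account.

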Levine and Turner conducted a retrospective analysis of 32 children with active CD who were treated with an 8 week course of combined azithromycin and metronidazole identical to the dosage proposed in this trial: azithromycin was given 7.5–10 mg/kg, once daily (maximal dose: 500 mg), for five consecutive days/ week for 4 weeks, and 3 times a week for the following 4 weeks, in conjunction with metronidazole. Azithromycin-based therapy was applied due to its effect in inducing apoptosis (down regulation of anti-apoptotic transcription factor Bcl-xL), efficacy against biofilms and intracellular bacteria. Clinical remission was observed in 21/32 (66%) patients and 54% of children with elevated CRP at baseline normalized their C-reactive protein (CRP).³⁵

More recently, Levine et al. performed a randomized controlled trial (NCT01596894) allocating children with mild to moderately active disease into groups receiving azithromycin + metronidazole therapy (7.5mg/kg azithromycin once daily for five consecutive days/ week for 4 weeks, and 3 times a week for the following 4 weeks, in conjunction with 20mg/kg/day of metronidazole) or metronidazole alone daily for 8 weeks.²¹ The results of this trial show that remission rates with azithromycin + metronidazole

therapy are better than with metronidazole alone, with a 66% clinical remission. There were no drug-related serious adverse events (SAEs) in the study.

Personalized adjunctive antibiotic therapy in pediatric Crohn's disease treatment

We have recently shown that the use of immunomodulators and the need for treatment escalation to anti-TNF or surgery are comparable after 6 years of follow-up, following induction of remission using either exclusive enteral nutrition (EEN) or steroids, both of which are used as 'standard-of-care' induction therapy in pediatric CD.³⁶ We also showed that a baseline (B) fecal microbiome signature with predominance of Proteobacteria, does not correct with nutritional therapy by week 12 and is associated with recurrence of disease.³⁷ We have recently shown, in an independent cohort of CD patients, that remission due to nutritional therapy corrects features of the dysbiosis described in the study by Gevers et al. in the RISK-CCFA cohort of treatment naïve pediatric CD.³⁸

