5 STUDY POPULATION

5.1 INCLUSION CRITERIA

In order to be eligible to participate in this study, an individual must meet all of the following criteria:

1. Provision of signed and dated informed consent form (and assent form, as applicable)
2. Stated willingness to comply with all study procedures and availability for the duration of the study
3. Male or female, aged 3 to 17 years
4. Diagnosed with CD according to standard clinical and histological criteria, within 36 months of week 0

5. Exhibiting mild to moderate symptoms of active disease, as determined by a PCDAI score >10 (or >7.5 excluding the height item) and ≤37.5
6. Evidence of active inflammation based on either: fecal calprotectin level >=250 microgram/g (local laboratory or pre-arranged sponsor testing) within 30 days prior to week 0 visit; or according to accepted endoscopic and histologic evidence obtained during an endoscopy procedure completed within 30 days prior to Week 0 Visit.

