9.4.3 ANALYSIS OF THE SECONDARY OUTCOME VARIABLE(S)

In secondary outcome analyses, the effects of treatment with antibiotics on the microbiome will be assessed to determine whether the signature of group A2 can be modified to move closer to group B.

If this is the case, then groups A2 and B will be pooled and compared against A1. If the microbiome shifts associated with antibiotic use do not make A2 more similar to group B, then groups A1 and B will be pooled and compared against A2 to assess whether there is an additional immune-regulatory effect of azithromycin (in combination with metronidazole) to influence disease flare risk.

Data for secondary outcome variable analysis are independent of the primary outcome variable and will be collected at each study visit.

Continuous secondary outcomes will be summarized at each visit for both the observed values and the changes from baseline. A linear mixed model with timepoint, group, their interaction and baseline as covariates will be used to assess the difference in means between groups at each timepoint. An AR(1) covariance structure will be assumed and the Kenward-Roger degrees of freedom approximation will be utilized. Least squares estimates for the population mean and standard deviation will be provided at each assessment timepoint by group. Missing values will not be imputed. Due to the exploratory nature of the assessments, no correction for multiplicity will be made.

Categorical secondary outcomes variables will be analyzed similarly to the primary outcome (Section 9.4.2).

The analysis of the secondary efficacy parameters will be based on the ITT population.

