9.4.5 DEMOGRAPHIC AND BASELINE DESCRIPTIVE STATISTICS

Demographic and baseline characteristics will be based on the Intent-to-Treat (ITT) population. For evaluations which are performed at both the screening and baseline visits (Visit 2), baseline values are to be taken from the baseline visit.

Baseline characteristics to be compared between treatments will include age, gender, age at diagnosis, disease location and behavior (classified using the Paris classification scheme), disease activity (PCDAI score), CRP values, FCP values, and anthropometrics including height and weight z-score.

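### CRP and calprotectin normalization have no baseline condition, so children never abnormal at entry count as normalized; improvement as any fall has no minimum and says little for PCDAI

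*Combined protocol and SAP*

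**What the plan says.** Section 9.1 lists two kinds of yes/no marker outcome at weeks 4, 12, 24, 36 and 52.

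- **Normalization.** "Normalization (yes vs no) of C-Reactive Protein (CRP; < 0.5 mg/dL) and fecal calprotectin" is judged by the visit value alone; the calprotectin cut-off is below 250 µg/g. A parallel PCDAI outcome uses a score below 10.
- **Improvement.** "Improvement (yes vs no) of C-Reactive Protein (change in CRP < 0 mg/dL) and fecal calprotectin" means any negative change. The PCDAI version is "Improvement (yes vs no) of disease activity (change in PCDAI < 0) rate at weeks 4, 12, 24, 36, and 52".

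Section 9.4.3 analyses categorical secondary outcomes like the primary, that is, by Fisher's exact test. It adds: "The analysis of the secondary efficacy parameters will be based on the ITT population". Section 9.3 defines that set as all randomized participants.

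Section 5.1 has no CRP criterion. It asks for "Evidence of active inflammation based on either: fecal calprotectin level >=250 microgram/g" "or according to accepted endoscopic and histologic evidence obtained during an endoscopy procedure completed within 30 days prior to Week 0 Visit". It also requires a PCDAI above 10 (or above 7.5 without the height item) and at most 37.5. Under sections 4.1 and 9.2, a child with PCDAI above 10 at week 4 is not randomized. For measures taken at both screening and week 0, section 9.4.5 states that "baseline values are to be taken from the baseline visit".

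**The concern.** The word normalization implies a change from abnormal to normal, but the definition measures status at the visit. A child with a normal CRP throughout is a success at every visit whatever the treatment. The retrospective series cited in section 2.2 used the narrower denominator: "54% of children with elevated CRP at baseline normalized their C-reactive protein (CRP". A rate in all randomized children is not comparable with that figure.

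The improvement outcomes have the opposite weakness. With no minimum fall, calprotectin going from 1500 to 1490 µg/g is a success. A normal CRP that is unchanged, for example below the reporting limit twice, is a failure on improvement and a success on normalization. For PCDAI, selection into the randomized groups nearly fixes the answer at week 4.

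At stake is whether these secondary rates can be read as evidence of biochemical remission or of maintained disease control.

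**Working it through.** **The plan's own figure.** The only sample-size figure with inputs is 25 per arm for the later larger trial (section 9.2: flare 80% vs 40%, 80% power, 10% dropout; two-sided 0.05 from section 9.4.1). With p̄ = 0.6:

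n = [1.96·√(2·0.6·0.4) + 0.842·√(0.8·0.2 + 0.4·0.6)]² / 0.4² = 22.33

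22.33/0.9 = 24.8, so 25 per arm. It reproduces. It concerns the primary outcome, and no figure is stated for CRP or calprotectin.

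**Who can be normal at entry.**
- CRP: any child, since no criterion refers to it.
- Calprotectin: the entry threshold (250 or more) is the exact complement of the normal range (below 250). Only a child who enters by endoscopy, or whose separate week 0 value has fallen below 250, can be normal at baseline. Note b to the schedule in section 1.3 says week 0 samples are not repeated if given at screening, which narrows the second route.

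**Effect on the normalization contrast.** Let q be the share normal at entry, s1 and s2 the proportions of these who are normal at the visit (A1, A2), and r1 and r2 the rates among children abnormal at entry.

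Difference = q(s2 − s1) + (1 − q)(r2 − r1)

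Assumptions, not in the documents: r1 = 20% and r2 = 60%, borrowing the size of the 40-point contrast in section 9.2.

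*Case 1: entry-normal children stay normal in both arms (s1 = s2 = 1).* The difference is 40(1 − q) points. The last two columns give exact Fisher power, taking 25 randomized per arm.

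| q | A1 vs A2 | Difference (points) | n per arm for 80% power | Power, all randomized | Power, abnormal at entry only |
|---|---|---|---|---|---|
| 0 | 20% vs 60% | 40 | 23 | 79% | 79% (25 per arm) |
| 0.2 | 36% vs 68% | 32 | 38 | 57% | 65% (20 per arm) |
| 0.4 | 52% vs 76% | 24 | 62 | 33% | 45% (15 per arm) |
| 0.6 | 68% vs 84% | 16 | 111 | 16% | 25% (10 per arm) |

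*Case 2: entry-normal children flare and antibiotics protect them.* At q = 0.4:
- s = 60% vs 90%: 0.4·30 + 0.6·40 = 36 points.
- s = 40% vs 80%: 0.4·40 + 0.6·40 = 40 points, so no dilution.

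**Pilot size.** Twenty children are divided over groups A, B and C, so an arm has at most 10. At 10 per arm, power is about 25% even with q = 0.

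**Chance imbalance.** Two extra entry-normal children in an arm of 10 move its rate by (2/10)(1 − r), where r is the rate among abnormal children: 20 points if r = 0, 10 if r = 50%, 4 if r = 80%.

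**PCDAI improvement.** A child who enters above 10 and is randomized at 10 or below has a negative change at week 4 by construction. The only exceptions are children who enter by the no-height-item route with a score of 10 or less. Later, a child who entered at 37.5 and rises from remission to 30 has a change of 30 − 37.5 = −7.5. That counts as improved, although 30 is above the remission limit of 10.

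**The case against.** Several stronger readings are tempting, and the documents do not support them.

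- **The treatment contrast is diluted.** A reader might infer this as a fact. It needs entry-normal children to stay normal in both arms. The trial is about maintaining remission, so these children may themselves carry a contrast (case 2).
- **CRP and calprotectin are equally affected.** They are not: the calprotectin entry threshold closes most of the gap.
- **Stable normal children always fail improvement.** Only those whose value does not fall do so. A CRP going from 0.4 to 0.3 mg/dL is a success on both outcomes.
- **Flares go uncounted.** They do not. The child at PCDAI 30 fails the PCDAI-below-10 outcome at that visit and, if still there at week 52, the primary outcome.
- **A chance imbalance of two children is worth 20 points.** That is a ceiling, reached only if no abnormal child normalizes.

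Three further objections carry weight. First, baseline-adjusted mixed models of the continuous measures remain in section 9.4.3, and the Netherlands addendum lists these outcomes as exploratory. Second, a baseline-abnormal denominator restores the 40-point difference but only part of the power. Third, antibiotics start at week 4. A child abnormal at week 0 but normal by week 4 would still count as normalized, so conditioning on week 0 alone does not isolate the antibiotic effect.

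None of this removes the definitional gap.

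**Conclusion.** The point holds as a defect of definition. Never-abnormal children count as normalized, mainly for CRP. Improvement has no minimum fall. PCDAI improvement is near 100% at week 4 by design and can later score a child who has lost remission as a success.

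The loss in the risk difference is the factor 1 − q only if entry-normal children stay normal in both arms: 40 points becomes 32, 24 or 16 at q = 0.2, 0.4 or 0.6. Neither q nor the behaviour of entry-normal children is in the documents, so the size is unknown and may be nil. The figures also model A1 against A2. Section 9.4.3 plans contrasts that pool non-randomized group B with one of these arms, where the entry-normal share could differ for reasons other than chance.

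The primary outcome and the sample size are untouched, and in this pilot the practical effect is small. The main reason to act is section 12: if feasibility is adequate, the protocol goes forward without substantial change and the pilot data can be included in the full-scale trial.

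**What to change.** In section 9.1:

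1. Report CRP and calprotectin normalization among randomized children at or above the cut-off (0.5 mg/dL; 250 µg/g) at the week 0 baseline, and state the denominator. Also report it by week 4 status.
2. Keep normal at visit, in all randomized children, as a separately named outcome.
3. Drop the PCDAI any-fall outcome in favour of the existing PCDAI outcome at each visit, and align its cut-off (below 10) with the 10-or-below used elsewhere in the protocol.
4. For CRP and calprotectin improvement, either drop the outcome or set a minimum fall with a rule for values below the reporting limit. Which of the two is a matter of preference.
5. Reconcile the CRP cut-off with section 8.1, which also allows the local reference range, because the new denominator depends on it.

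The change is one of wording and uses data already collected. The cost is a smaller denominator for the two normalization rates: at q = 0.6, an arm of 10 leaves about 4 children.
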